8.5.4. Vital Signs

Vital signs and change from baseline will be summarized descriptively at each visit by treatment group.

8.5.5. HbA1c, Serum Chemistry and Hematology

Shift tables (i.e., normal, abnormal not-clinically significant, abnormal clinically significant at baseline versus normal, abnormal not-clinically significant, abnormal clinically significant at follow-up in a 3-by-3 contingency table) will be provided to assess changes in laboratory values from baseline to follow-up result at each scheduled follow-up visit. Determinations of clinical significance will be made by the individual study centers based on their laboratory normal ranges. The counts and percentage of subjects with each of the 9 possible "shift" outcomes will be calculated by treatment group. Individual laboratory data from scheduled and unscheduled visits will be listed.

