The secondary efficacy endpoints will be based on the change in the average 24-hour pain score from baseline to the 6-month follow-up [Day 180] (3 months after the Day 90 injection) obtained from the Daily Pain and Sleep Interference Diary. The difference in the mean of the change in the average 24-hour pain score will be compared between the treatment group and the placebo arm to determine the treatment effect in the efficacy populations. The proportion of subjects with at least a \geq 50% reduction in the average 24-hour pain score from baseline to the 6month follow-up [Day 180] (3 months after the Day 90 injection) will be compared between the two study groups.

All other efficacy endpoints will be exploratory.

SAFETY

Any subject who receives study injections (VM202 or placebo) will be included in the safety analysis population. Adverse events (including serious adverse events, and adverse events leading to treatment discontinuation) throughout the 9-month follow-up will be described according to severity and to their relationship with the study drug and injection procedure. Descriptive statistics (N, mean, median, SD, minimum and maximum values, where applicable) will be used to characterize continuous safety parameters. Categorical variables will be summarized by counts and by percentage of subjects in corresponding categories.

All subjects will undergo testing as presented in the American Cancer Society Cancer Screening Guidelines as part of their screening to rule out cancer.

KINETICS

PHARMACO- HGF serum levels will be determined immediately pre-treatment on Day 0, immediately pre-treatment on Day 14, on Day 21, Day 60, immediately pre-treatment on Day 90, immediately pre-treatment on Day 104, Day 111, Day 150, Day 180 and Day 270.

> The number of copies of VM202 in whole blood will be determined at Day 0 (pre-injection, and 2 hours [\pm 1 hour] post injection), at Day 14 (pre-injection, and 2 hours $[\pm 1 \text{ hour}]$ post injection), Day 21, Day 60, at

Day 90 (pre-injection, and 2 hours [\pm 1 hour] post injection), at Day 104 (pre-injection, and 2 hours [± 1 hour] post injection), Day 111, Day 150, Day 180, and Day 270.

TABLE OF CONTENTS

Investi	GATOR'S AGR	EEMENT	3
STUDY S	SYNOPSIS		4
TABLE O	OF CONTENTS.		13
ABBREV	IATIONS		17
PERSON	NEL AND FACI	LITIES	19
1. Bac	CKGROUND		23
1.		Diabetic Peripheral Neuropathy	
		Pathophysiology of Diabetic Peripheral Neuropathy	
1.1		reatment Options	
1	1.2.1.		
		Medical Management	
	1.2.3.		

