1.2.1. PREVENTIVE TREATMENT

Glycemic control. It is generally agreed that long-term complications of both type 1 and type 2 diabetes can be reduced by tight glycemic control. To date, this is the only intervention specifically shown to arrest or postpone the onset and severity of peripheral neuropathy.²⁷⁻²⁹

Modifiable risk factors. The incidence of neuropathy is also associated with potentially modifiable cardiovascular risk factors, including an elevated triglyceride level, a high body mass index (BMI), smoking, and hypertension.³⁰

Foot care. Patients with diabetes also need to be educated about foot care and footwear, and about protection of hyposensitive areas and pressure points, to prevent the occurrence of ulcers and to decrease the risk of bone infection.³¹

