8. STATISTICAL METHODS

8.1. General Principles of Data Analyses

The primary analysis for this study will be performed and summarized after all randomized subjects have had an opportunity to complete their 9-month follow-up visit.

The primary analyses of the safety endpoints will be based on the Safety population. The primary analyses of the efficacy endpoints will be based on the ITT population. Additional sensitivity analyses for the primary and secondary efficacy endpoints will be performed to further assess the effects of the treatment (Section 8.4.4).

The statistical analyses will be reported using summary tables, figures and listings. Continuous variables will be summarized with means, standard deviations, medians, minimums, maximums, 25th percentiles, 75th percentiles, and number of non-missing observations for each treatment group.

Categorical variables will be summarized by counts and by the percentage of subjects in corresponding categories.

All inferential statistical analyses will be performed with a two-sided confidence level of 95% or a two-sided significance level of 0.05 unless otherwise noted.

All analyses and tabulations will be performed using SAS[®] Version 9.4 or higher on a Server platform.

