8.5. Safety Analyses

Safety analyses in this study will evaluate the safety profile of VM202, as compared with control. No formal statistical testing will be conducted for the safety analyses. The following sections summarize the descriptive analysis methods for these safety endpoints. All subjects in the Safety population will be included in these analyses. Subjects will be grouped by treatment administered. All summaries will be derived based on available data. No imputation will be performed for missing values.

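### SAP 8.5.5 summarises HbA1c and laboratory values only by a site-judged 3-by-3 shift table, so a between-arm change that stays within a category could be missed

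*SAP*

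**What the plan says.** SAP 8.5.5 covers HbA1c, serum chemistry and hematology together. Its one summary is a set of shift tables, baseline against follow-up, that "will be provided to assess changes in laboratory values from baseline to follow-up result at each scheduled follow-up visit". The three categories are normal, abnormal not clinically significant (NCS) and abnormal clinically significant (CS), and the nine cells are counted by treatment group. On who sets the categories it says: "Determinations of clinical significance will be made by the individual study centers based on their laboratory normal ranges". For the values themselves: "Individual laboratory data from scheduled and unscheduled visits will be listed".

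Three other places bear on this.

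- Protocol Synopsis, Safety: "Descriptive statistics (N, mean, median, SD, minimum and maximum values, where applicable) will be used to characterize continuous safety parameters".
- SAP 8.1, the general default: "Continuous variables will be summarized with means, standard deviations, medians, minimums, maximums, 25th percentiles, 75th percentiles, and number of non-missing observations", for each treatment group.
- SAP 8.5.4, immediately before 8.5.5: "Vital signs and change from baseline will be summarized descriptively at each visit by treatment group".

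SAP 4.4 lists HbA1c, serum chemistry and hematology as safety outcomes. Protocol 4.2.4 has them measured at local laboratories at Screening and Days 0, 90, 180 and 270.

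**The concern.** These are continuous measurements, and the only planned summary turns each into one of three labels. That loses three things.

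- **Size.** Every subject has diabetes and is on medication for it, and HbA1c up to 10.0% is allowed at entry (Protocol 3.3.1). Most HbA1c values will probably be abnormal at every visit; that is an inference. A rise from 7.5% to 9.5% stays in one cell if the center gives both values the same label.
- **Direction.** Abnormally high and abnormally low share a row and a column. Potassium, glucose or platelets going from high to low count as no shift when both values carry the same NCS or CS label.
- **A common scale.** A laboratory range separates normal from abnormal. It does not separate NCS from CS, and 8.5.5 gives no criterion. Up to 30 sites decide for themselves.

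At stake is the ability to see a moderate drift in HbA1c, ALT, creatinine, platelets or white cells by arm. The data to show it will have been collected at three follow-up visits.

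**Working it through.** **1. The sections side by side**

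| Place | Method | Value or change summarised by arm? |
|---|---|---|
| Protocol Synopsis, Safety | N, mean, median, SD, min, max, where applicable | Yes, in general terms |
| SAP 8.1 | Mean, SD, median, quartiles, min, max, n | Yes, as a default |
| SAP 8.5.1, exposure | Descriptive statistics for continuous variables | Yes |
| SAP 8.5.4, vital signs | Value and change from baseline | Yes |
| SAP 8.5.5, laboratory | 3-by-3 shift table plus listings | Not stated |

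SAP 8.5 introduces its subsections with "The following sections summarize the descriptive analysis methods for these safety endpoints", so the method named in each subsection reads as the method for that endpoint. SAP 8.3 does not help: HbA1c and laboratory values are not among the baseline characteristics to be summarised, and characteristics not named there are only listed.

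**2. The arm sizes used below**

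Protocol 6.1 and SAP 5 give 286 and 143 evaluable subjects (difference 1.0, SD 3.0, 90% power, two-sided 0.05, ratio 2:1). By the normal approximation, placebo n = (1.960 + 1.282)² × 3.0² × (1 + 1/2) / 1.0² = 141.8, so 142 and 284. The stated 143 and 286 agree within rounding and give power 0.902. With 10% dropout, 429 / 0.90 = 476.7, so 477. No figure in the documents is disputed.

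**3. Precision of a mean-change summary**

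The documents give no SD for HbA1c change, so it is assumed. The 95% half-width is 1.96 × SD × √(1/286 + 1/143) = 1.96 × SD × 0.1024.

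- SD 0.8: 0.16 points
- SD 1.0: 0.20 points
- SD 1.2: 0.24 points
- SD 1.5: 0.30 points

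**4. What the shift table would show for the same change**

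This is a simulation on assumed inputs: baseline mean 7.6 and SD 1.2, kept between 5 and 10; SD of change 1.0; upper limit of normal 6.0; one common CS cut-off for all sites; 1,000 runs. HbA1c in the VM202 arm is set 0.5 points higher purely as a test case.

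| CS cut-off | Moved to a worse category, placebo / VM202 | Chance that this contrast gives p<0.05 |
|---|---|---|
| 8 | 15.3% / 25.2% | 0.69 |
| 9 | 13.3% / 23.1% | 0.70 |
| 10 | 7.8% / 14.1% | 0.48 |
| 12 | 2.9% / 4.5% | 0.09 |

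Mean change on the same data exceeds 0.99 throughout. For a 0.3-point difference the table gives 0.06 to 0.30 and mean change 0.81 to 0.85.

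**5. Using both directions of the table**

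The contrast in step 4 ignores moves to a better category, so it understates the table. Score worse +1, same 0, better −1. At cut-off 8:

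- VM202: better = 1 − 0.252 − 0.654 = 0.094; net 0.158.
- Placebo: better = 1 − 0.153 − 0.663 = 0.184; net −0.031.
- SE = √[(0.252 + 0.094 − 0.158²)/286 + (0.153 + 0.184 − 0.031²)/143] = 0.0589.
- z = 0.189 / 0.0589 = 3.21, so the chance of p<0.05 is about 0.89.

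The same steps give z = 3.12, 2.65 and 1.93 at cut-offs 9, 10 and 12 (chance 0.88, 0.76 and 0.49). For mean change, z = 0.5 / 0.1024 = 4.88. The squared ratio is (3.21/4.88)² = 0.43 at best and (1.93/4.88)² = 0.16 at worst. Under these assumptions even a full reading of the table keeps roughly 16% to 43% of the information. The p<0.05 criterion is only a yardstick here; no safety test is proposed.

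**The case against.** **The SAP 8.1 default already covers laboratory values.** It can be read that way. But 8.5.5 does not refer to it, 8.5 presents the subsection methods as the safety methods, and 8.5.1 and 8.5.4 state continuous summaries where they are wanted. What stands is that this is an ambiguity inside the SAP as well as a shortfall, and it needs resolving.

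**The protocol is not contradicted.** The sentence is in the synopsis and is qualified by applicability. Protocol 6.3.4 requires no particular statistics, and Section 6 defers detail to the SAP. That supports calling it a shortfall rather than a violation. The qualifier gives little cover for plainly continuous variables.

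**Effects would still surface.** A reader might infer that no table could show a drug effect on HbA1c. The documents do not support that. The shift table is by arm at each visit with ordered categories, and step 4 shows visible movement at three of four cut-offs. Clinically significant abnormal results also fall within the adverse event definition (Protocol 5.1). SAP 8.5.3 tabulates treatment-emergent events, with subsets of the Investigations class among those of special interest. The DSMB sees unblinded safety output. What remains exposed is mainly sub-threshold change.

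**HbA1c as a rival explanation for the pain result.** A reader might infer this from Protocol 1.2.1, which says of tight glycemic control that "this is the only intervention specifically shown to arrest or postpone the onset and severity of peripheral neuropathy". That concerns the onset and severity of neuropathy over the long term. It says nothing about pain scores within 90 days, so the point rests on safety reporting alone.

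**Local laboratories make pooled means awkward.** True: units must be harmonised first. That is a reason to keep the site-judged table, not to have it alone.

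**Conclusion.** The point holds as a shortfall in safety reporting. SAP 8.5.5 names only a site-judged shift table and listings, less than the synopsis promises, less than 8.5.4 gives for vital signs, and without applying 8.1. A between-arm change in HbA1c or another analyte that stays within categories could be missed; large or threshold-crossing effects may still be seen.

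The size is illustrative. The half-width of 0.16 to 0.24 HbA1c points rests on an assumed SD of 0.8 to 1.2 and on 286 and 143 subjects, which are the targets for Day 90 pain data and not the safety population or the laboratory counts expected at Days 180 and 270. The simulation rests on an assumed HbA1c distribution and one common CS cut-off, whereas the plan leaves that judgement to each center. No efficacy inference is affected.

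**What to change.** In SAP 8.5.5:

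1. For HbA1c and each analyte, add observed value and change from baseline by arm at Days 90, 180 and 270 (n, mean, SD, median, quartiles, minimum, maximum), with units harmonised across local laboratories.
2. Add low/normal/high shift tables based on each laboratory's range.
3. Optionally, give the between-arm difference in mean HbA1c change with a descriptive 95% CI and no formal test, in keeping with SAP 8.5.
4. Keep the NCS/CS table as a supplement.

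The cost is SAP wording, a few extra tables on data already collected, and the unit harmonisation. No new assessments are needed.

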8.5.6. Prior and Concomitant Medications of Interest

Prior medications are those medications taken within 60 days of the first injection of study drug. Concomitant medications are those medications taken after the initial dose of study drug. A medication with a missing start date and a stop date that is either missing or on or after the treatment start date will be considered as concomitant. All prior and

concomitant medications will be assigned preferred drug names using WHODrug Global B3 (March 2018 version or later). Prior and concomitant medications of interest will be determined by the CDRC and will be summarized separately for each treatment group by preferred names. These summaries will present the number and percentage of subjects using each medication.

8.5.7. Retinal Fundoscopy

Retinal fundoscopy findings in each eye (presence or absence of proliferative retinopathy, other finding) at screening (baseline), 6-month, and 9- month follow-up visits and any changes from the baseline at the follow-up visits will be summarized descriptively by treatment group.

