3.5.2. DISCONTINUED SUBJECTS

Any subject may voluntarily discontinue the study at any time without prejudice. The investigator may discontinue a subject from the study at any time if (s)he considers that remaining in the study compromises the subject's health or the subject is not sufficiently cooperative. In either event, reason(s) for discontinuation should be recorded on the study worksheets.

Possible reasons for study discontinuation include the following:

- Adverse events (AEs) necessitating discontinuation from the study (pretreatment).
- The subject is lost to follow-up.
- Subject decision (specify).
- Investigator decision (specify).
- Other reason (specify).

The reasons for any subject discontinuation will be recorded on the study completion form of the study worksheets.

Additional subjects may be enrolled if subjects discontinue (investigational treatment) prior to the 90-day visit in order to achieve a 477 subject dataset with 90 day data (primary efficacy endpoint).

Subjects discontinued for AE(s) will be followed-up after subject's discontinuation until the event is resolved or considered medically stable by the investigator.

Subjects who withdraw prior to study completion will undergo the following if possible:

- Retinal Fundoscopy
- Concomitant Medications
- · Serum Chemistry and Hematology
- Vital Signs
- Serum HGF
- Copies of VM202
- Injection site reaction assessment if discontinued prior to Day 150
- Adverse Events

[figure not shown]
In case of a subject lost-to-follow-up, the investigator must do his/her best to contact the subject (by phone or letter) at least twice. If no response is obtained from the subject, the investigator is encouraged to contact one of the subject's relatives or his/her general practitioner. Documentation of these contacts must be recorded in the subject medical chart. It can be, for instance, the acknowledgement of receipt of a letter sent to the subject.

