4.2.1. RETINAL FUNDOSCOPY

Proliferative retinopathy, defined as the presence of new proliferating blood vessels (neovascularization) arising from the retina or optic disc and growing on the retinal surface or into the vitreous cavity, will be assessed by retinal fundoscopy at Screening for eligibility and repeated at Day 180 and Day 270. Retinal fundoscopy must be performed by an ophthalmologist within 3 months of Screening.

In cases where fundoscopy alone is deemed insufficient to determine eligibility, fluorescein angiography may be conducted at Screening.

4.2.2. **CONCOMITANT MEDICATIONS**

Concomitant medications will be recorded at each visit using the trade name or generic name as described in Section 3.7.

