PROCEDURE	Screening / Baseline	1 st Inj Daj			jection 4 ± 1 D	Day 21 ± 3 D	2M Day 60		njection 90 ± 7 D		jection s after D 90	Day 111 7 ± 3 Days after 4 th
	(-90 – 0 D)	Pre-dose	Post- dose*	Pre- dose	Post- dose*	100	± 3 D	Pre- dose	Post- dose*	Pre- dose	Post- dose*	Injection
Visit Number	1	2			3	4	5		6		7	8
Baseline Evaluation							С. 					
Informed Consent	~							-			0	
Medical History	~	~										
Physical Exam	✓											
Symptoms of BPNS	 ✓ 											
Cancer Screening [†]	 ✓ 			1							ļ. l	
Viral Screening - HIV, HTLV, HBV, HCV	~										i. i	
ECG	✓											
Urine Pregnancy Test	✓											
Retinal Fundoscopy	✓										1	
Safety and Efficacy Parameters												
MNSI	✓											
VAS	✓	~						~				
Daily Pain and Sleep Interference Diary	✓							~				
HbA1c	~	~		1				~			1	
Serum Chemistry and Hematology	~	~						1				
Vital Signs	~	~	~	~	~	~	~	~	~	~	×	~
Concomitant Medications	~	 ✓ 		~		~	~	~		~		✓
BPI-DPN	3.	 ✓ 						~			[]	
Semmes-Weinstein Filament Test		~						~) []	
PGIC								-				
Study Injections		✓		~				~		1		
Copies of VM202 in whole blood		~	~	~	~	~	~	~	~	✓	~	✓
Serum HGF		✓		~		~	~	~		✓		~
Nerve Conduction (only at select sites)		✓										
Tylenol Usage				~		 Image: A start of the start of	~	~		 ✓ 		✓
Treatment												
Injection Site Reaction Assessment			~	~	~	~	~	~	~	×	× .	~
Adverse Events			~	~	~	 Image: A second s	1	~	1	✓	1	1

† Cancer screening: chest X-ray or chest CT scan if subject has a previous history of tobacco use within 3 months; pap smear and mammogram within past 12 months (females only); for subjects \geq 50 years old, fecal occult blood test. * 2 hours after injection (± 1 hour)

TABLE 1 SCHEDULE OF EVALUATIONS AND	VISITS (CONTINUEI))
--	-------------------	----

Procedure	5M Day 150 ±7 D	6M Day 180 ±7 D	9M Day 270 ± 14 D	Early Withdrawal
Visit Number	9	10	11	
Safety and Efficacy Parameters				
Vital Signs	~	✓	~	\checkmark
Concomitant Medications	\checkmark	✓	✓	✓
Retinal Fundoscopy		\checkmark	✓	\checkmark
VAS		\checkmark	✓	
MNSI		~	~	
Daily Pain and Sleep Interference Diary		✓	✓	
BPI-DPN		✓	✓	
PGIC		\checkmark	✓	
Semmes-Weinstein Filament Test		✓	✓	
Nerve Conduction (only at select sites)		✓	~	
HbA1c		✓	✓	
Serum Chemistry and Hematology		✓	✓	✓
Study Injections				
Copies of VM202 in whole blood	~	✓	~	\checkmark
Serum HGF	✓	✓	✓	✓
Tylenol Usage	✓	✓	✓	✓
Treatment				
Injection Site Reaction Assessment	✓			√1
Adverse Events	✓	✓	✓	✓

1 If withdrawal occurs before Day 150 Visit

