7.2. Visit Windows

Data at each scheduled follow-up visit will be analyzed according to the nominal visit identified on the data record.

In case of multiple different visits with the same nominal visit designation, the visit with the visit date closest to the target days of each protocol specified visit schedule (Table 3) will be used for the efficacy analyses. For visits with the same distance to the target days, the later nominal visit record will be used. Data from the other visits (if any) will be provided in data listings only.

					100.00	1.1.013				
VISIT	1 st INJECTION	2 ND INJECTION	DAY 21	Month 2	3 RD INJECTION	4 ^{тн} Injection	DAY 111	MONTH 5	MONTH 6	Month 9
TARGET DAY	0	14	21	60	90	104	111	150	180	270

TABLE 3.	Target	Day

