8.5.3. Adverse Events

All adverse event summaries will be restricted to Treatment Emergent Adverse Events (TEAE), which are defined as AEs that occur after dosing and pre-existing medical conditions that worsen following exposure to an investigational product. An AE with a missing start date and a stop date that is either missing or on or after the treatment start date will be considered as a TEAE. For summary purposes, verbatim terms reported by the study centers will be mapped to MedDRA (v21.0 or later) system organ classes (SOC) and preferred terms by the CRO and approved by the CDRC. It should be noted that only AEs that occurred after the first injection will be collected during the study.

The adverse event listings will be displayed by treatment group. The number of subjects experiencing a particular event, the percentage of subjects experiencing the event, and the total number of events will be presented. The following summaries will be created:

- TEAE by SOC and preferred term;
- TEAE by SOC, preferred term and protocol version;
- TEAE by SOC, preferred term and maximum severity. At the across-SOC and preferred term levels of subject summarization, a subject is classified according to the highest severity if the subject reported one or more events; severity within an SOC is not summarized. AEs with missing severity will be considered severe for this summary;
- TEAE by SOC, preferred term and closest relationship to study treatment (Related/Not Related). At each level of subject summarization, a subject is classified according to the closest relationship if the subject reported one or more

events. AEs with a missing relationship will be considered related for this summary; events classified as 'possibly', 'probably' or 'definitely' will be considered 'related'.

- Serious TEAEs by SOC and preferred term;
- TEAEs leading to study discontinuation by SOC and preferred term;
- Adverse events of special interest (AESI) by preferred term. Specific areas of special interest to be presented separately are for dizziness, somnolence, weight increase, peripheral edema, and falls as well as subsets of events within the Nervous System disorders, Investigations, and Injury, Poisoning and Procedural Complications system organ classes. The specific preferred terms within these subsets will be determined at the blinded data review.
- Injection Site Reactions (ISRs) included under AESI will include designations of relatedness and severity.

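### SAP 8.5.7 has no row for the early-withdrawal fundoscopy, the only planned post-dose eye exam for dosed subjects who leave before Day 180 (minor, cheap to fix)

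*SAP*

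**What the plan says.** Fundoscopy is a named safety outcome (SAP 4.4). Protocol 4.2.1 sets its schedule: proliferative retinopathy "will be assessed by retinal fundoscopy at Screening for eligibility and repeated at Day 180 and Day 270". Protocol 3.5.2 adds one more occasion. It says "Subjects who withdraw prior to study completion will undergo the following if possible", and fundoscopy is the first item on the list that follows. The schedule of evaluations in the protocol and Table 1 of the SAP (Section 3) both tick fundoscopy in the column headed "Early Withdrawal".

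The analysis text is narrower. SAP 8.5.7 covers "Retinal fundoscopy findings in each eye (presence or absence of proliferative retinopathy, other finding) at screening (baseline), 6-month, and 9- month follow-up visits", together with changes from baseline at those follow-up visits, described by treatment group. SAP 7.2 sets the visit rule: "Data at each scheduled follow-up visit will be analyzed according to the nominal visit identified on the data record". For the safety section as a whole, SAP 8.5 says "All summaries will be derived based on available data".

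**The concern.** The SAP's own schedule includes an exam that its summary does not tabulate. For most subjects the loss is small: someone who leaves after Day 180 already has the 6-month exam in the table. A dosed subject who leaves before Day 180 contributes a screening value and nothing else, even if an ophthalmologist examined the eyes at withdrawal.

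The outcome is linked to the mechanism. Protocol 1.3 describes HGF as a strong angiogenic factor, and Protocol 4.2.1 defines proliferative retinopathy by new vessel growth. The plan guards against it by exclusion at entry (criterion 13) and by repeat exams. At stake is whether the one systematic by-arm count of eye findings uses every exam done for that purpose.

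**Working it through.** **Where the exam is collected and where it is counted**

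- Screening: collected, and tabulated in SAP 8.5.7.
- First dose to Day 180: no fundoscopy scheduled.
- Day 180 and Day 270: collected, and tabulated as 6 and 9 months.
- Early withdrawal: collected where possible, with no row in SAP 8.5.7.

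**Whether another rule brings the withdrawal exam in**

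1. SAP 7.2 assigns data by nominal visit. The schedule gives the early-withdrawal column no visit number, and the target-day table has no entry for it. The closest-to-target rule handles only duplicate records with the same nominal visit, and only for efficacy analyses.
2. The available-data sentence in SAP 8.5 sets how missing values are handled. It does not add a time point to the list in 8.5.7.
3. SAP 8.1 says "The statistical analyses will be reported using summary tables, figures and listings", so the exam may be listed. A listing is not a count by arm. SAP 8.5.5 expressly commits to listing unscheduled laboratory results; 8.5.7 has no matching sentence.
4. SAP 8.5.3 tabulates "TEAE by SOC and preferred term". This is the one remaining route to a by-arm count, and it needs the investigator to report the finding as an AE. Protocol 5.1 counts clinically significant investigation results as AEs, but it excludes changes in a chronic disease that fit its natural course. No eye category is named among the AEs of special interest.

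**How many subjects**

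The only anchor in the documents is the dropout allowance (SAP 5).

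- Needed with 3-month data: 286 + 143 = 429.
- Randomized: 429 / (1 − 0.10) = 476.7, rounded up to 477, split 2:1 as 318 and 159. This reproduces the plan's figure.
- Allowance: 477 − 429 = 48, that is 318 − 286 = 32 on VM202 and 159 − 143 = 16 on placebo.

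The 48 does not bound the group of interest on either side.

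- It can be too high. A subject with fewer than 5 of 7 diary days has no 3-month score (SAP 7.7) yet may stay and attend Day 180. The 7 subjects withdrawn before dosing (SAP 6, footnote 1) may fall within it, leaving 48 − 7 = 41. The withdrawal exam needs an ophthalmologist (Protocol 4.2.1), is done only where possible, and will be missed by subjects who refuse or cannot be reached (Protocol 6.4).
- It can be too low. Departures between Day 90 and Day 180 lie outside it, and Protocol 3.5.2 allows extra enrolment to replace subjects who discontinue before the 90-day visit.

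For scale only, and as an assumption: if 5% to 20% of 477 left before Day 180, that would be 0.05 × 477 = 24 to 0.20 × 477 = 95 subjects (16 to 64 on VM202, 8 to 32 on placebo). Fewer of them would have a post-dose withdrawal exam.

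**The case against.** The strongest reply is that little can slip through. Proliferative retinopathy is excluded at entry and checked by fundoscopy, so disease first seen after dosing is a new finding. All AEs are recorded regardless of severity (Protocol 5.2), every treatment-emergent AE is tabulated by arm, and all reported AEs go to an unblinded DSMB (Protocol 6.3.6, SAP 7.5). It is hard to see why an investigator would call new vessel growth natural progression in a trial that excluded it and looks for it again. Summarising by scheduled visit is also the SAP's general style: the laboratory shift tables and nerve conduction summaries do the same, and it keeps exposure comparable within a row. The biological concern is tempered as well. In the phase II study serum HGF stayed fairly constant (Protocol 1.6.4), and Protocol 1.6.6 considers VM202 active only at the injection site. A subject who leaves before Day 90 has had at most half the planned dose.

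Most of this stands, and it sets the weight of the point at minor. It does not close the gap. The AE route rests on individual judgement in a population where diabetic eye disease can progress on its own, whereas a systematic exam summary does not depend on that judgement.

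A reader might infer that withdrawal eye findings are lost or kept from safety oversight. The documents do not support that: the exam is collected, may be listed, and a reported event reaches both the AE tables and the DSMB.

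**Conclusion.** The point holds as a minor, inexpensive improvement. SAP 8.5.7 leaves a collected, mechanism-linked safety exam out of the by-arm summary, and nothing else in the SAP puts it back. A new finding at that exam is counted by arm only if it is reported as an AE, which is likely for new proliferative retinopathy but not assured.

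The size is unknown. It would be tempting to take 48 as the number affected and multiply it by an assumed risk. The 48 is an allowance for missing 3-month data, and the documents give no rate of new proliferative retinopathy, so no expected case count can be stated. Nor do the documents show that withdrawal exams would differ by arm, so bias between arms should not be inferred. The effect is limited to the completeness of a descriptive safety count. No efficacy endpoint, error rate or power figure changes.

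**What to change.** Amend SAP 8.5.7 as follows.

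1. Keep the per-eye by-visit table and add an early-withdrawal row by treatment group in the Safety population. This alone closes the gap.
2. As a supplement, add one subject-level row per arm: the number and percentage of subjects without proliferative retinopathy at screening who have it in either eye at any post-baseline exam (Day 180, Day 270 or early withdrawal). The denominator is such subjects with at least one post-baseline exam.

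The cost is a few lines of SAP text and two table rows from data already collected, with no new procedure. The downside is that both rows mix lengths of follow-up and amounts of exposure. They should be read beside the by-visit table and do not replace it.
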